10.2 Data and Safety Monitoring Plan

The Data Safety and Monitoring Committee (DSMC) of the University of Kansas Cancer Center will provide annual review of this trial

The DSMC monitors data management and subject safety. Subject accrual is reviewed annually by the Protocol Review and Monitoring Committee of the University of Kansas Cancer Center. The DSMC also provides advice on the overall conduct of the study. Meetings will be held on an annual basis. Interval conference calls may be conducted as required. The functions of the DSMC are primarily those of an overview nature in regard to both data and safety, as detailed below.

All data collected for this trial will ultimately reside in a central trial specific database. Data accuracy and completeness will be monitored via inspection of summary reports prepared for the DSMC by the biostatistician for this project.

The subject cohort consists of essentially healthy women who are defined as being at high risk for the development of breast cancer, but do not have any clinical evidence of or suspicion for an

existing malignancy. As such, side effects that might be due to the study intervention are expected to be minimal but should be easily identified and monitored.

In regard to adverse events (AEs) or serious adverse events (SAEs), it is not deemed necessary for the DSMC to address these for individual subjects. Rather, all grade 4 toxicities are reported as an SAE to the institutional review board immediately.

In addition to the functions performed by the DSMC, an External Advisory Board (EAB) will serve in a general advisory role in regards to assessing the progress that is being made on the study. Subject accrual rates, and specifically problems with accrual that might impact on the ability of the trial to be completed, can be addressed by the EAB. Likewise, the EAB may make suggestions on other aspects that would improve the quality of the trial. The EAB consists of two individuals with experience in clinical prevention trial: [name]., of Mayo Clinic, Rochester, MN; and [name], of Johns Hopkins University, Baltimore, MD.

10.3 FDA Monitoring

The FDA may monitor/audit various aspects of the study. These monitors will be given access to facilities, databases, supplies and records to review and verify data pertinent to the study.

10.4 Record Retention

Clinical records for all participants, including CRFs, all source documentation (containing evidence to study eligibility, history and physical findings, laboratory data, results of consultations, etc.), as well as IRB records and other regulatory documentation will be retained by the Protocol Lead Investigator ([name]) in a secure storage facility in compliance with HIPAA, OHRP, FDA regulations and guidances, and NCI/DCP requirements unless the standard at the site is more stringent. The records will be maintained, at a minimum, for two (2) years after completion of the study. The records should be accessible for inspection and copying by authorized persons of the Food and Drug Administration.

11.0 STATISTICAL METHODS

The study is a Phase II, double-blind, randomized, placebo-controlled clinical trial to assess the potential efficacy of SDG as a chemopreventive agent, as measured by changes in proliferation index (Ki-67) between baseline and 12 months. Secondarily, the study will evaluate other pharmacodynamic properties of the agent and assess which biomarkers, if any, are modulated. Side effects, adverse events, and quality of life will also be assessed.

Standard randomization strategies will be employed. Institutional site and whether the woman is on or not on oral contraceptives will be the only stratification factors, so that each site can be provided with a unique randomization schedule at initiation. All eligible subjects will be randomly assigned to SDG or placebo in a planned 2:1 ratio.

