11.1 Sample Size and Power

The primary outcome of interest is efficacy of SDG relative to the placebo, thus the pre- to post-treatment change in a proliferation index (percent of cells expressing Ki-67) is the basis of the power analyses. From our pilot study, the average percentage of cells expressing Ki-67 at baseline was 4%, and the average change in percent of cells expressing Ki-67 was a 2.4% reduction, for subjects meeting similar eligibility requirements as used in this trial.

A 2:1 randomization of 220 evaluable subjects will provide 83% power to detect a 2.5% reduction in Ki-67 for the treatment group compared to no reduction in the control group; this will be our primary endpoint. This is based on an assumption of a common standard deviation of 6% for change in Ki-67 in both groups and a Type I error rate of 5%. Within the target of 220 evaluable subjects, we expect to recruit 72 women taking oral contraceptives (OC) and 148 women not taking OCs. Because the efficacy of SDG is unknown for OC users, we considered different scenarios and evaluated the average effect in the SDG arm and the corresponding power. For 0-70% efficacy of SDG among OC users, the respective average Ki-67 reduction range from 1.7% to 2.3% will result in a statistical power ranging from 50% to 76%.

Ki-67 reduction in SDG arm (non-OC)	Efficacy of SDG in OC	Ki-67 reduction in SDG arm (OC)	Ki-67 reduction in SDG arm (OC & non-OC avg.)	Power
2.5%	0%	0%	1.7%	50%
2.5%	20%	0.5%	1.8%	55%
2.5%	50%	1.3%	2.1%	68%
2.5%	70%	1.8%	2.3%	76%
2.5%	100%	2.5%	2.5%	83%

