11.2 Statistical Analysis

All analyses will be intent-to-treat. All subjects randomized will be evaluable for safety and all subjects that have both a pre and post specimen are evaluable for efficacy. Primary analysis of efficacy will be performed on all evaluable subjects and secondary analysis will be done on those subjects who received at least 6 months of study medication and were confirmed as being in the follicular phase for both RPFNA procedures. From our experience we have very little missing data; however, if the missing data rate is above 5%, we will use multiple imputation to impute these values to perform the primary and secondary analyses.

The primary outcome will be change in Ki-67 (percent of cells expressing Ki-67) from baseline to 12 months. The two-sample t-test will be used to compare the change in Ki-67 between the SDG

and placebo groups. Any difference in baseline values of Ki-67 between the two groups would be due to chance, however, if there is a significant difference, then analysis of covariance adjusting for baseline values will be performed. Due to potential skewness in these variables we will assess whether or not the Central Limit Theorem may be assumed. Given the sample size the existence of an extremely high degree of skewness would require the use of the Wilcoxon Signed Rank test.

For the secondary endpoints, similar methods as above will be used to compare the treatment and control groups at two time points for all markers, i.e., serum hormones and clinical laboratory tests. We will also correlate change in the primary biomarker Ki-67 with change in other markers (e.g., bioavailable estradiol, cytokines, RTqPCR results) using Pearson's correlation coefficient. Again, if there exists a high degree of skewness in these variables, Spearman's correlation will be utilized.

Multiple regression analysis will also be used to investigate whether changes in Ki-67 are due to variables other than treatment effect (e.g., age, cytromorphology, Gail risk; as well as the predictive effect of other biomarkers on modulation of Ki-67). Best subsets and stepwise approaches will be employed while controlling for treatment group.

For comparison of moderate or worse toxicities we will consider grade 3 toxicity or premature trial discontinuation as the critical events. The prevalence of events in the SDG vs. the placebo arm will be examined by Fisher's exact test.

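### SDG efficacy in oral-contraceptive users is called unknown and they are a third of the evaluable women, yet no Ki-67 effect by contraceptive stratum is planned

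*Combined protocol and SAP*

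**What the plan says.** Section 11.0 states that "Institutional site and whether the woman is on or not on oral contraceptives will be the only stratification factors", with the purpose given as "so that each site can be provided with a unique randomization schedule at initiation". On method it says only that "Standard randomization strategies will be employed". Section 4.6.3 has OC users draw study IDs from the opposite end of each site's list.

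Section 11.1 expects 72 OC users and 148 non-users among 220 evaluable women. It continues: "Because the efficacy of SDG is unknown for OC users, we considered different scenarios". Its table runs from 50% pooled power (no effect in OC users) to 83% (full effect). Section 3.0 says OC users became eligible about 2.5 years after study start and expects this to extend the reach of a positive result. Section 2.4.3 records that the pilot excluded OC users, partly because a biomarker change might be harder to show in them.

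For the primary outcome, section 11.2 says: "The two-sample t-test will be used to compare the change in Ki-67 between the SDG" and placebo groups. If baseline Ki-67 differs between arms, "if there is a significant difference, then analysis of covariance adjusting for baseline values will be performed". Extreme skewness "would require the use of the Wilcoxon Signed Rank test". The regression paragraph gives age, cytomorphology and Gail risk as examples. The correlative analyses name BMI, age and SNPs as modifiers. OC use appears in neither list.

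**The concern.** The plan raises a question at the design stage and then has no analysis that addresses it. By its own table, the pooled test is as likely as not to succeed when SDG does nothing in a third of the women. A positive result therefore cannot by itself support applying SDG to OC users, which is one of the two stated reasons for admitting them. A null result could not be told apart from dilution. The pilot has no OC users to draw on, and a split made after the data are seen would be post hoc.

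There are two lesser matters. The primary test uses neither stratification factor and changes form if a baseline significance test is positive. The rank test named for extreme skewness is for paired data and does not compare two independent arms.

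**Working it through.** **Inputs.** Section 11.1: SD of change 6, effect 2.5 points, 220 evaluable women, 72 OC and 148 non-OC. Sections 11.0 and 11.2: 2:1 allocation, two-sided 5%. Arm sizes are therefore about 147 vs 73 overall, 99 vs 49 non-OC and 48 vs 24 OC.

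**Reproducing the plan.** SE = 6 × √(1/147 + 1/73) = 0.859. Noncentral-t power at 2.5 is 82.6% (stated 83%). With no effect in OC users the average effect is 2.5 × 148/220 = 1.68, and power is 49.6% (stated 50%). Using the table's rounded averages, all five rows reproduce within 2 points.

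**Precision by stratum.** SE = 6 × √(1/n₁ + 1/n₂), and half-width = t × SE.

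| Contrast | SE | 95% half-width | Power at 2.5 |
|---|---|---|---|
| Non-OC (99 vs 49) | 1.05 | 2.07 | 66% |
| OC (48 vs 24) | 1.50 | 2.99 | 38% |
| Interaction, √(1.05² + 1.50²) | 1.83 | 3.61 | 27.5% |

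The interaction row is the power to detect complete loss of a 2.5-point effect in OC users.

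**What the OC estimate would tell us.** Simulated trials, arms balanced 2:1 within strata, 2.5-point effect in non-users. Results are conditional on a significant treatment effect in a model adjusted for OC use, which is not the protocol's t-test.

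| Efficacy in OC users, relative to non-users | 0% | 20% | 50% | 70% | 100% |
|---|---|---|---|---|---|
| OC estimate below 1.25 | 67% | 55% | 37% | 27% | 14% |
| OC 95% CI includes zero | 95% | 92% | 83% | 74% | 57% |

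With zero effect in OC users, their CI still includes 2.5 in about 81% of these trials. The estimate shifts clearly between the extremes but separates neighbouring scenarios poorly.

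**Cost of leaving OC use out of the t-test.** The documents give no OC difference in mean Ki-67 change, so shifts of up to 3 points either way are assumed (200,000 simulated trials per scenario).
- Type I error at a 3-point shift: 4.4 to 4.5% if arms are balanced within strata, about 5.0% if assignment is unblocked.
- Power loss with a common 2.5-point effect: at most 1.2 to 1.7 points (balanced) or 1.8 to 1.9 (unblocked).
- The loss reaches 4.5 to 4.7 points only if SDG has no effect in OC users and their change is shifted 3 points towards less reduction. In the other direction it is under 1 point.

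**Baseline and site terms.** With baseline Ki-67 in the model, residual SD = 6 × √(1 − r²). At assumed r = 0, 0.3 and 0.5, power at 2.5 is 82.6%, 85.9% and 91.7%. Site terms work the other way if site is not prognostic: simulation with an assumed 5 to 10 sites and r = 0 gave about 80 to 82%. The number of sites is not stated.

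**The case against.** Heterogeneity was considered: section 11.1 tabulates it, and section 3.0 assumes the same SD in both OC groups. For a phase II trial asking a pooled question, that may be the place it matters most. The regression covariates are only examples, and exploratory analyses at 5% are allowed, so an OC analysis is unspecified rather than barred. All of that stands. It does not close the gap, because an OC main effect kept by stepwise selection is not a treatment effect by stratum.

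A subgroup of 72 is underpowered. This also stands, and it is why the estimates should be descriptive. A reader might infer from the 67% versus 14% contrast that a stratum estimate would resolve the question. The intermediate scenarios, and the 81% of intervals that still include the full effect, show that it rarely would.

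A reader might also infer that a t-test ignoring the stratification factors is invalid. It is not. It is slightly conservative if arms are balanced within strata, and near 5% if assignment is unblocked; the documents mention no blocks. The stated reason for stratifying is logistical, which weakens the case for a site term in particular.

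**Conclusion.** The gap is real and should be corrected. The documents treat the SDG effect in a third of the sample as unknown, stratify on that factor, expect wider applicability from including these women, and plan no estimate of the effect in them. What is lost is interpretation; the primary test remains valid.

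The precision figures rest on the plan's SD of 6 in both strata and the expected 148/72 split. A pre-specified OC estimate, at about ±3.0 points, would inform the reading of the result but would rarely decide it. Adjusting for OC use is a small efficiency gain over a range of shifts that had to be assumed. The site effect cannot be sized.

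It is tempting to treat 83% as a floor once covariates are added. That fails if non-prognostic site terms are included, and 83% in any case assumes the full effect in OC users. The signed rank wording is a separate, definite error.

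**What to change.** 1. **Main change.** Pre-specify the SDG-placebo difference in Ki-67 change with 95% CI in each OC stratum (status as randomised), and the treatment-by-OC estimate. Use the same evaluable set and imputations as the primary analysis, and label all of it descriptive. State the half-widths (about 2.1, 3.0 and 3.6), the interaction power of about 27.5%, and the table above showing how rarely the OC estimate settles the matter alone. Note that OC status is partly confounded with calendar time, because OC users entered only from about 2.5 years after start. This affects comparisons between strata, not the randomised contrast within each.
2. **Primary model.** Replace the t-test and the conditional ANCOVA with one pre-specified linear model of Ki-67 change on treatment, baseline Ki-67 and OC status. A site term is optional, with small sites pooled by a rule fixed before unblinding. It may cost 1 to 2 power points if site is not prognostic, so do not present 83% as a minimum if it is included. Say that 83% assumes the full effect in OC users.
3. **Rank test.** Replace the signed rank test with a two-sample rank test (rank-sum, or van Elteren stratified by OC use), keeping the role the plan gives it under extreme skewness.

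The cost is wording and a few model degrees of freedom. The data are already collected, and sample size and randomisation do not change.

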11.1 Sample Size and Power

The primary outcome of interest is efficacy of SDG relative to the placebo, thus the pre- to post-treatment change in a proliferation index (percent of cells expressing Ki-67) is the basis of the power analyses. From our pilot study, the average percentage of cells expressing Ki-67 at baseline was 4%, and the average change in percent of cells expressing Ki-67 was a 2.4% reduction, for subjects meeting similar eligibility requirements as used in this trial.

A 2:1 randomization of 220 evaluable subjects will provide 83% power to detect a 2.5% reduction in Ki-67 for the treatment group compared to no reduction in the control group; this will be our primary endpoint. This is based on an assumption of a common standard deviation of 6% for change in Ki-67 in both groups and a Type I error rate of 5%. Within the target of 220 evaluable subjects, we expect to recruit 72 women taking oral contraceptives (OC) and 148 women not taking OCs. Because the efficacy of SDG is unknown for OC users, we considered different scenarios and evaluated the average effect in the SDG arm and the corresponding power. For 0-70% efficacy of SDG among OC users, the respective average Ki-67 reduction range from 1.7% to 2.3% will result in a statistical power ranging from 50% to 76%.

Ki-67 reduction in SDG arm (non-OC)	Efficacy of SDG in OC	Ki-67 reduction in SDG arm (OC)	Ki-67 reduction in SDG arm (OC & non-OC avg.)	Power
2.5%	0%	0%	1.7%	50%
2.5%	20%	0.5%	1.8%	55%
2.5%	50%	1.3%	2.1%	68%
2.5%	70%	1.8%	2.3%	76%
2.5%	100%	2.5%	2.5%	83%

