2.4.3 Eligibility criteria for SDG pilot study

Eligibility criteria included regular menstrual cycles, no oral contraceptives, a 3-fold or greater increase in 5-year estimated risk for breast cancer relative to SEER statistics for age group, and normal mammogram performed in the follicular phase of the menstrual cycle within 3 months of baseline RPFNA. Subjects on oral contraceptives were excluded in order to reduce subject hormonal heterogeneity and because it might be more difficult to demonstrate biomarker modulation from SDG in the face of exogenous hormones. Baseline RPFNA was also to be performed in the follicular phase and had to show unequivocal hyperplasia +/- atypia as well as a minimum Ki-67 expression of 2% in hyperplastic ducts. The Ki-67 value of 2% was chosen since this is the median Ki-67 value in hyperplastic tissue obtained by RPFNA from high risk pre-menopausal women in the follicular phase of the cycle [86]. Further, a Mayo Clinic series suggests that women having a biopsy showing atypical hyperplasia and a Ki-67 of 2% or higher have a significantly higher 10-year risk of breast cancer (14% versus 3%) [88]. The early-mid follicular phase is utilized due to greater subject comfort and less bleeding during RPFNA.

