2.4.4.2. Change in Ki-67 and cytomorphology

Thirty-six (80%) of the 45 evaluable subjects demonstrated a decrease in Ki-67, from a median of 4% (range 2-16.8%) to 2% (range 0-15.2%) ($p<0.001$ by Wilcoxon signed rank test). A decrease from baseline in the proportion of women with atypical cytology from 62% to 42% ($p=0.035$) was also observed.

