3.0 SUMMARY OF STUDY PLAN

The favorable outcome of the pilot study suggests progression to a Phase II multi-institutional placebo-controlled trial of 12 months of Brevail® (50 mg SDG) in moderate and high risk premenopausal women. Modulation of Ki-67 in women with baseline Ki-67 of 2% or greater in hyperplastic tissue is the primary endpoint rather than normalization of atypia, so as to limit the number of women who would need to be screened by RPFNA to 2-3 for every woman going on trial (vs. 4-5 if all had to have atypia). Other risk biomarkers will be measured, as well as impact on quality of life, change in breast pain in those with mastalgia at baseline, and surrogate markers of fertility. These considerations will be important for eventual uptake of SDG as a prevention agent. Mechanisms of action will also be explored. Similar eligibility criteria are used as in the pilot study, where the average percentage of cells expressing Ki-67 at baseline was 6.4% (median 4%) with an average change of -3.7% with a common standard deviation of 5.5%.

The study eligibility is being altered approximately 2.5 years after study start to allow inclusion of women on oral contraceptives. This will both widen application of results should they be positive and is expected to at least double the rate of accrual. Assessment of difference in change in Ki-67 between women randomized to SDG versus placebo can be accomplished with a 2:1 randomization of 242 women. Assuming a dropout rate of 10%, with 220 evaluable subjects there will be 83% power to detect a 2.5% reduction in Ki-67 for the treatment group compared to no reduction in the control group; this will be our primary endpoint. This is based on an assumption of a common standard deviation of 6% for change in Ki-67 in both the no oral contraceptive and oral contraceptive groups and a Type I error rate of 5%

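### The 83% power holds only for a net SDG–placebo difference of 2.5 points; entry on a single Ki-67 reading makes some placebo fall likely, and two conflicting pilot changes leave the adequacy of 220 women open

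*Combined protocol and SAP*

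**What the plan says.** Section 11.1 gives the power as "83% power to detect a 2.5% reduction in Ki-67 for the treatment group compared to no reduction in the control group", and adds: "This is based on an assumption of a common standard deviation of 6% for change in Ki-67 in both groups". The scenarios tabulated there vary only how well SDG works in oral-contraceptive users. No row allows for a change on placebo.

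On entry, section 3.0 states: "Modulation of Ki-67 in women with baseline Ki-67 of 2% or greater in hyperplastic tissue is the primary endpoint". Sections 4.4.1 and 4.4.3 apply the 2% threshold to the screening RPFNA, and the schedule in 6.1 shows no further aspirate before treatment. One reading is thus both the eligibility screen and the baseline. Section 2.4.3 explains the 2% threshold: "this is the median Ki-67 value in hyperplastic tissue obtained by RPFNA from high risk pre-menopausal women in the follicular phase".

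The single-arm pilot used the same threshold, and its results are reported in two ways. Section 3.0 has "Ki-67 at baseline was 6.4% (median 4%) with an average change of -3.7% with a common standard deviation of 5.5". Section 11.1 has "at baseline was 4%, and the average change in percent of cells expressing Ki-67 was a 2.4% reduction".

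In section 11.2 the primary analysis is a two-sample t-test on change. Analysis of covariance on baseline is used only if the arms differ significantly at baseline, although the same paragraph says any such difference would be due to chance.

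**The concern.** Women selected because one reading lies in the upper half of a distribution will, on average, read lower next time even without treatment, unless the measurement repeats perfectly. Here it does not: the plan itself allows an SD of change of 6 points in both arms. A placebo change of exactly zero is therefore an optimistic reference value, and section 11.1 does not discuss it.

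The pilot had no control arm, so its fall mixes any drug effect with any selection effect. It is also the only stated empirical basis for the size of effect, and it is quoted with two different values. The cost would be a trial with less power than advertised. Randomization applies the same selection to both arms, so the estimated difference would not be biased.

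**Working it through.** **Inputs.** 220 evaluable, 2:1, SD of change 6 (11.1); two-sided 5% (end of 11.2); entry at 2% or above (3.0, 4.4.3); population median 2% (2.4.3); at least 500 cells scored (4.4.3, Appendix 1 section 5.3); pilot change 3.7 (3.0) or 2.4 (11.1). All Ki-67 figures are percentage points.

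**Reproducing the plan's figure.** With 147 and 73 women, SE = 6 × √(1/147 + 1/73) = 0.859. The noncentrality is 2.5 / 0.859 = 2.91, and the noncentral t on 218 df gives 82.6%. The table in 11.1 also reproduces: differences of 1.7, 1.8, 2.1 and 2.3 give 50, 55, 68 and 76%. There is no arithmetic error.

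**What the 83% refers to.** Power depends only on the net difference:

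net = (SDG-arm fall) − (placebo-arm fall).

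80% power needs a net difference of 2.42 at SD 6. If 2.5 is the total SDG-arm fall, a placebo fall above 2.5 − 2.42 = 0.08 takes power below 80%. If the SDG arm falls by 3.7, the margin is 3.7 − 2.42 = 1.28.

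**Is a placebo fall expected?** Binomial counting error alone on 500 cells is √(0.02 × 0.98 / 500) = 0.6 points at 2%, and √(0.04 × 0.96 / 500) = 0.9 points at 4%, before any variation between aspirates. Readings are therefore not perfectly repeatable. With a cut at the population median, the expected change from selection is downward. Its size depends on the repeat correlation and on the Ki-67 distribution in unselected women, and the documents give neither.

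**Power over assumed placebo falls (SD 6).** The falls are illustrative. Each cell shows the net difference, then power.

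| SDG-arm fall | Placebo 0 | Placebo 0.3 | Placebo 0.6 | Placebo 1.0 |
|---|---|---|---|---|
| 2.5 (planned) | 2.5: 83% | 2.2: 72% | 1.9: 60% | 1.5: 41% |
| 2.4 (pilot, 11.1) | 2.4: 79% | 2.1: 68% | 1.8: 55% | 1.4: 37% |
| 3.7 (pilot, 3.0) | 3.7: 99% | 3.4: 98% | 3.1: 95% | 2.7: 88% |

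**Pilot figures side by side.** Section 3.0 gives a mean baseline of 6.4, a median of 4 and an average change of −3.7. Section 11.1 gives an average baseline of 4 and an average change of −2.4. Section 2.4.4.2 reports the pilot baseline median as 4%, so the 4 in 11.1 matches the median and not the mean. The 2.4 might then be a median change or a subset figure; the documents do not say.

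**Analysis.** If baseline and change have correlation r, ANCOVA reduces the SD from 6 to 6 × √(1 − r²). Selection on baseline makes a non-zero r likely. The plan gives no value for r. As an illustration only, r = 0.3 in absolute value gives 6 × √0.91 = 5.72, and power for a net 2.5 rises from 83% to 86%.

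**The case against.** The strongest reply is that the 83% is a conditional statement and is true as written. Section 11.1 opens by describing efficacy relative to placebo, so 2.5 can be read as the net difference to be detected. Against the 3.7 of section 3.0, 2.5 would already leave 1.2 points for a placebo fall. The same section also shows readers powers of 50 to 76% for differences of 1.7 to 2.3, so low power near a net of 2 is disclosed, though for another reason.

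Much of this stands. It does not settle the matter, because the table labels 2.5 as the reduction in the SDG arm and equates zero efficacy with zero reduction. The documents nowhere say that 2.5 was discounted from 3.7, and the other pilot figure, 2.4, leaves no room for a discount.

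A reader might go further and infer that the plan's own figures imply a placebo fall of about 0.3 to 0.6 and true power of 58 to 70%. They do not. Such values need an assumed lognormal distribution, no drift over 12 months, and the planning SD of 6 turned into a repeat correlation. A gamma model with the entry mean at 6.4 and an SD near 6 gives a fall of about 1.6 and power near 17%, and other fits cannot reach an SD of 6.

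Nor does the pilot pattern ("from a median of 4% (range 2-16.8%) to 2% (range 0-15.2"%, with 80% of women falling) confirm that lognormal model. At the correlations it needs (0.67 to 0.82), selection alone would leave a 12-month median of 3.4 to 4.0, with 60 to 63% falling. An assumed correlation of 0.5 does not help either, because its own SD of change would be 6.8 to 8.7, not 6.

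**Conclusion.** The point holds as a matter of power and precision, not of bias or arithmetic. The 83% is right for a net difference of 2.5 at SD 6. Some placebo fall is expected because one imperfectly repeatable reading, cut at the stated population median, serves as both screen and baseline. This assumes no opposing upward drift over 12 months. The direction is well supported; the amount cannot be derived from the documents.

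If 2.5 is the whole SDG-arm fall, placebo falls of 0.3 to 1.0 would reduce power to about 72 to 41%. If the SDG arm falls by 3.7, the same placebo falls leave 98 to 88%. Whether 220 evaluable women are enough therefore turns on the unreconciled pilot change and on whether 2.5 was meant as net or gross. This should be fixed, with medium confidence.

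**What to change.** 1. In 11.2, make ANCOVA of 12-month Ki-67 (or of change) on baseline Ki-67 the primary analysis, whatever any test of baseline difference shows. Both readings are already collected.
2. Reconcile the pilot baseline and change in 3.0 and 11.1. For each figure, say whether it is a mean or a median, and whether it covers all 45 evaluable women or a subset.
3. In 11.1, state that 83% applies to a net difference of 2.5, and say whether 2.5 is a discounted pilot effect or a minimum effect of interest. Keep zero placebo change as the reference case and add power for placebo falls of 0.3, 0.6 and 1.0, labelled as illustrative.

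The cost is one line in 11.2, one reconciled statement of the pilot data that the sponsor holds, and one small table. No patients, visits or assays are added. The stated power becomes a range, which may lie below 83%, or above it if 3.7 proves to be the mean change.
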